3 SCHEDULE OF ASSESSMENTS

The schedule of assessments is in Table 3-1. All visits will be scheduled relative to the Day 1 Visit in this study.

Assessments may be performed in any order when more than 1 assessment is required at a particular time point, unless noted otherwise. All assessments should be performed before study drug dosing (Section 9.6), unless noted otherwise.

Table 3-1 Study VX20-445-119: Treatment Period and Safety Follow-up Visit								
Event/ Assessment ^a	Treatment Period					ETT Visit ^b	Safety Follow-up Visit (28 ± 7 Days After Last Dose of Study Drug ^c)	Comments
	Day 1 ^d	Weeks 4, 8, 16, 24 (± 5 Days)	Weeks 12, 20, 28, 32, 40, 44, 52, 56, 64, 68, 76, 80, 88, 92 (± 5 Days)	Weeks 36, 48, 60, 72, 84 (± 5 Days)	Week 96 (± 10 Days)			
Clinic visit	X	X		X	X	X	X	See Section 9.1.6 for use of remote measures in extenuating circumstances.
Telephone contact			X					Assess subject's status, any AEs, concomitant medications, treatments, and procedures.
ICF and assent	X							
Safety and Efficacy Assessments								
CFQ-R	X	X		Weeks 48, 72	X			Completed before the start of any other assessments (Section 11.2.4).
Ophthalmologic examination				Week 48 (± 4 weeks)	X (- 4 weeks)	X (- 4 weeks)	X (- 4 weeks)	Subjects will have an ophthalmologic examination at the completion of study participation (defined in Section 9.1.5). This examination should be completed at or up to 4 weeks before the relevant study visit (Section 11.4.6).
Height and weight	X	X		X	X	X	X	Measured with shoes off (Section 11.4.4).
Vital signs and pulse oximetry	X	X		X	X	X	X	Performed after subject has been at rest for at least 5 minutes (Section 11.4.3).
Physical examination (PE)	X				X	X		Symptom-directed PEs may be performed at any time if deemed necessary by the investigator (Section 11.4.3).

^a All assessments will be performed before dosing unless noted otherwise.

^b If the subject prematurely discontinues study drug treatment, an ETT Visit should be scheduled as soon as possible after the decision to discontinue treatment (Section 9.1.3).

^c The Safety Follow-up Visit is required for all subjects, unless otherwise specified. For subjects who complete an ETT Visit 3 weeks or later following the last dose of study drug, the ETT Visit will replace the Safety Follow-up Visit (Section 9.1.2).

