^d The Day 1 Visit should be on the same day as the last scheduled visit of the parent study (Section 9.1.1). Subjects whose Day 1 Visit is NOT within 1 day of the last scheduled visit of the parent study will repeat all Day 1 assessments. Subjects whose Day 1 Visit is within 1 day of the last scheduled visit of the parent study will NOT have to repeat any Day 1 assessments that were specified to be performed at the last scheduled visit in the parent study.

Table 3-1 Study VX20-445-119: Treatment Period and Safety Follow-up Visit									
Event/ Assessment ^a	Treatment Period					ETT Visit ^b	Safety Follow-up Visit (28 ± 7 Days After Last Dose of Study Drug ^c)	Comments	
	Day 1 ^d	Weeks 4, 8, 16, 24 (± 5 Days)	Weeks 12, 20, 28, 32, 40, 44, 52, 56, 64, 68, 76, 80, 88, 92 (± 5 Days)	Weeks 36, 48, 60, 72, 84 (± 5 Days)	Week 96 (± 10 Days)				
Standard 12-lead ECG	X	Weeks 8, 16, 24		Weeks 48, 72	X	X	X	Performed prior to any procedure that may affect heart rate (e.g., blood draws) and after subject has been at rest for at least 5 minutes (Section 11.4.5).	
Sweat chloride	X	X		Weeks 48, 72	X	X		Section 11.2.1	
Multiple-breath washout	X	X		Weeks 48, 72	X	X		Performed in multiple replicates, pre-bronchodilator, before the AM dose, and before spirometry assessment (Section 11.2.1).	
Spirometry	X	X		X	X	X	X	Performed pre-bronchodilator, before the AM dose, and at approximately the same time at each visit (Section 11.2.3).	
Pregnancy test	Urine	Serum	Urine	Serum	Serum	Serum	Serum	For all female subjects at telephone contacts, a urine pregnancy test will be performed with a home kit provided by the study site. Results of the home pregnancy test will be reported to the site by telephone (Section 11.4.2).	
Serum chemistry	X	X		X	X	X	X	Section 11.4.2	
Hematology	X	X		X	X	X	X		
Coagulation	X	Week 24		Weeks 48, 72	X	X			
Urinalysis	X			Week 48	X	X			
AEs and SAEs	Continuous from signing of the ICF through completion of study participation								Section 13.1; Completion of study participation is defined in Section 9.1.5.

Table 3-1 Study VX20-445-119: Treatment Period and Safety Follow-up Visit								
Event/ Assessment ^a	Treatment Period					ETT Visit ^b	Safety Follow-up Visit (28 ± 7 Days After Last Dose of Study Drug ^c)	Comments
	Day 1 ^d	Weeks 4, 8, 16, 24 (± 5 Days)	Weeks 12, 20, 28, 32, 40, 44, 52, 56, 64, 68, 76, 80, 88, 92 (± 5 Days)	Weeks 36, 48, 60, 72, 84 (± 5 Days)	Week 96 (± 10 Days)			

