8.2.2 Demographics and Baseline Characteristics

Demographics and baseline characteristics will be summarized based on the OL-FAS and presented by treatment group in the parent study and overall.

Demographic data from the parent study (445-116) will include the following:

- Age at parent study baseline (in years)
- Sex (female and male)
- Ethnicity (Hispanic or Latino, not Hispanic or Latino, and not collected per local regulations)
- Race (White, Black or African American, Asian, American Indian or Alaska Native, Native Hawaiian or Other Pacific Islander, multiracial, and not collected per local regulations)
- Country

Baseline characteristics from the parent study (445-116) will include the following:

- Weight (kg)
- Weight-for-age z-score
- Height (cm)
- Height-for-age z-score
- BMI (kg/m²)
- BMI-for-age z-score

Stratification categories used in the parent study will include the following:

- LCI_{2.5} at Screening Visit (<10, ≥10)
- Weight at Screening Visit (<30, ≥30 kg)

Disease characteristics from the parent study (445-116) baseline will include the following:

- Sweat chloride at parent study baseline (continuous)
- LCI_{2.5} at parent study baseline (continuous)
- ppFEV₁ category at parent study baseline (<70, ≥70 to ≤90, and >90)
- ppFEV₁ at parent study baseline (continuous)

- CFQ-R respiratory domain score at parent study baseline (child 6-11's version, continuous)
- Prior use of dornase alfa (Yes, No)
- Prior use of azithromycin (Yes, No)
- Prior use of inhaled antibiotic (Yes, No)
- Prior use of any bronchodilator (Yes, No)
- Prior use of any inhaled bronchodilator (Yes, No)
- Prior use of any inhaled hypertonic saline (Yes, No)
- Prior use of any inhaled corticosteroids (Yes, No)

Prior medication use definition is same as that for the baseline characteristics summary presented in the parent studies. In addition, data listings will also be provided for:

- Informed consent
- Inclusion/Exclusion criteria violation for subjects with any such violations

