8.3.3 Analysis of Additional Efficacy Variables

8.3.3.1 Definition of Variables

Percent predicted forced expiratory volume in 1 second (ppFEV₁): Percent predicted FEV₁ is the ratio of FEV₁ (L) and predicted FEV₁ (L), expressed as a percentage. The predicted FEV₁ will be calculated using the Global Lung Function Initiative¹ (GLI). See [Appendix C](#) for more details.

Cystic Fibrosis Questionnaire-Revised (CFQ-R): The CFQ-R^{3,4,5} is a validated CF-specific instrument that measures quality-of-life domains. This study utilizes four different versions of CFQ-R:

- CFQ-R for Children ages 6 to 11
- CFQ-R for Children ages 12 and 13
- CFQ-R for Adolescents and Adults (subjects 14 years and older)
- CFQ-R for Parents/Caregivers (subjects 13 years and younger)

In all four versions, specific question belonging to a domain is scored 1, 2, 3, or 4. The CFQ-R domain score, e.g., physical domain score or respiratory domain score, is defined as a scaled score as follows:

Scaled score for a domain = $100 \times (\text{mean (scores of all questions in the domain)} - 1)/3$,

where the score from a negatively phrased question is first reversed, i.e., reversed score = 5 – actual score, so that 1 always represents the worst condition and 4 the best condition. The (scaled) domain score ranges from 0 (worst condition) to 100 (best condition). The scaled score for a specific domain will not be calculated if more than half of the questions in the domain have missing scores.

The (scaled) domain score from the CFQ-R for Children ages 6 to 11, for Children ages 12 and 13, and for Adolescent and Adults will be pooled within and across subjects for the analysis purpose.

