8.3.3.2 Analysis Method

Absolute change in ppFEV₁ from baseline:

Analysis of this endpoint will be based on an MMRM similar to the analysis of the absolute change in SwCl. A descriptive summary of raw values and absolute changes from parent study baseline will also be presented.

The primary analysis will use the spirometry data obtained at clinic only. An additional analysis may be performed to include all available spirometry data obtained at clinic and obtained at home, if the spirometry data obtained at home are assessed to be reasonably consistent with the spirometry data obtained at clinic.

Absolute change in CFQ-R respiratory domain (RD) score from baseline:

Analysis of this endpoint will be based on an MMRM similar to the analysis of the absolute change in SwCl. A descriptive summary of raw values and absolute changes from parent study baseline will also be presented. In addition, the descriptive summary for raw values and the absolute change from parent study baseline of the parent version's CFQ-R RD score will be presented.

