- a. If no numerical measurement is available within a visit window, the measurement will be considered missing for the visit.
- b. If there is more than 1 numerical measurement available within a visit window, use the following rules:
 - i. The measurement closest to the target day will be used; or
 - ii. If there are multiple measurements with the same distance from the target day, the latest measurement will be used. If the latest measurement cannot be determined, then unscheduled visit will be selected

³For measurement collected on the date of first dose of study drug in Treatment Period, if it cannot be determined whether the measurement is before or after the first dose:

- a. Scheduled measurement will be treated as pre-dose observation.
- b. Unscheduled measurement will be treated as post-dose observation.

⁴Safety Follow-up analysis visit will be based on nominal Safety Follow-up visit. If a subject doesn't have a nominal Safety Follow-up visit but has an ETT visit with study day >687, then the ETT visit will be mapped into Safety Follow-up analysis visit.

Derived Variables:

1. Age (in years) at first dose date and post-baseline visit (for demographics, listing and the calculation of [percent] predicted spirometry variables):

Obtain the age at informed consent in parent study (in days) in “yy, mm” format (e.g., 24 years, 6 months) from the Vital Signs (VS) page at the Screening Visit, and add 0.5 month to convert to days.

Obtain the informed consent date.

Then age (in years) at first dose or post-baseline visit = [(first dose date or post-baseline visit date – informed consent date) in days + age at informed consent in parent study (in days)]/365.25.

2. Age (in months) at first dose or post-baseline visit (for use in calculation of BMI, height and weight z-score, as applicable):

Obtain the age at informed consent (in months) in parent study in “yy, mm” format (e.g., 24 years, 6 months) from Vital Signs (VS) page at the Screening Visit.

Obtain the informed consent date.

Then age (in months) at first dose or post-baseline visit = integer part of {(age at informed consent (in months) + 0.5 + diff (first dose or post-baseline visit date, informed consent date in parent study) in months)} + 0.5.

3. Missing first dose date or last dose date

If the first dose date is missing, use Day 1 visit date to impute.

Table 11-1 Analysis Visit Windows for Safety and Efficacy Assessments

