Appendix C: Details of GLI Equations for Calculating ppFEV₁

Percent predicted values will be calculated for parameters of FEV₁, FVC, FEV₁/FVC, and FEF_{25%-75%} using the Quanjer GLI-2012 Regression Equations and Lookup Tables.

The regression equations and lookup tables required to implement the Quanjer GLI-2012 predicted values are available in:

Philip H. Quanjer, Sanja Stanojevic, Tim J. Cole, Janet Stocks. Quanjer GLI-2012 Regression Equation and Lookup Tables (Version 7 April 2013). Global Lung Function Initiative. [online] Available at: <http://www.ers-education.org/home/browse-all-content.aspx?idParent=138978> [Accessed Mar 26, 2018].

The instructions and tools on how to implement the Quanjer GLI-2012 equations are:

Philip H. Quanjer, Sanja Stanojevic, Tim J. Cole, Janet Stocks. Implementing GLI-2012 regression equations (Version 19 July 2015). Global Lung Function Initiative. [online] Available at: <http://www.ers-education.org/home/browse-all-content.aspx?idParent=138979> [Accessed Mar 26, 2018].

Sanja Stanojevic. GLI-2012 - SAS Macro (Version 2, 7 April 2013). Global Lung Function Initiative. [online] Available at: <http://www.ers-education.org/home/browse-all-content.aspx?idParent=138988> [Accessed Mar 26, 2018].

Data handling rule for spirometry is as follows:

- Input age with at least 2 decimal places
- Height collected at the respective visit should be used; if the height at the respective visit is not available, the last non-missing record will be used.
- For race, map the CRF reported Black or African American to Black, all other races in CRF (except White) are mapped to 'other'; multiple checks for race in CRF are also mapped to 'other'; white is a reference race in the equations and assumes 0 values for all race coefficients in the GLI equations.

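### Carrying the last height forward in growing children overstates ppFEV₁ at the affected visits; the effect on visit means is probably small and the rule is cheap to replace

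*SAP*

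**What the plan says.** SAP 8.3.3.1 defines the outcome: "Percent predicted FEV₁ is the ratio of FEV₁ (L) and predicted FEV₁ (L), expressed as a percentage". Appendix C obtains the predicted values "using the Quanjer GLI-2012 Regression Equations and Lookup Tables" and lists how age, height and race are to be supplied. Height is taken from the same visit as the spirometry; failing that, "if the height at the respective visit is not available, the last non-missing record will be used". No maximum age is set for the carried record and no growth adjustment is made.

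Age is handled differently. Appendix A, under derived variables, defines "Age (in years) at first dose date and post-baseline visit (for demographics, listing and the calculation of [percent] predicted spirometry variables", so it advances with the visit date.

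In protocol Table 3-1, height and spirometry fall on the same visits: Day 1, Weeks 4, 8, 16, 24, 36, 48, 60, 72, 84 and 96, the ETT Visit and Safety Follow-up. SAP 8.3.3.2 restricts the main ppFEV₁ analysis to clinic spirometry, then adds: "An additional analysis may be performed to include all available spirometry data obtained at clinic and obtained at home", if home values are judged reasonably consistent with clinic values.

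**The concern.** Last observation carried forward is harmless for height in adults. Here, participants are aged 6 years or older, and the SAP's baseline table lists "CFQ-R respiratory domain score at parent study baseline (child 6-11's version, continuous" and no other self-report version. It is a fair inference that most were under 12 on entering the parent study and will grow through 96 weeks of treatment.

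When the rule applies, the two inputs to the prediction come apart: current age is paired with an old height. The shorter height lowers the denominator of ppFEV₁ and so raises the ratio. The error does not average out across children, because growth runs in one direction.

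The SAP otherwise imputes nothing unless it says so (8.1), and its MMRM uses no imputation (8.3.2.2). The height rule is nevertheless a single imputation that feeds the outcome. The SAP plans no count of how often it is used and no analysis without the affected values.

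**Working it through.** The documents give no figure to reproduce: no missing-height rate, growth rate or GLI coefficients. The calculation therefore rests on labelled assumptions.

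**Inputs from the documents**
- Scheduled gaps between clinic visits (protocol Table 3-1): 4 weeks up to Week 8, 8 weeks up to Week 24, then 12 weeks up to Week 96.
- ppFEV₁ = 100 × FEV₁ / predicted FEV₁ (SAP 8.3.3.1).

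**Assumptions**
- Growth g = 5–7 cm a year.
- Carried height h = 125–140 cm.
- At a given age, predicted FEV₁ is proportional to height^k, with k = 2.0–2.4.
- True ppFEV₁ = 90.

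**Formula.** With a gap of w weeks, true height is h + g × w/52.18. The relative overstatement of ppFEV₁ is

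((h + g × w/52.18) / h)^k − 1.

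**12-week gap**
- Low end (g = 5, h = 140, k = 2.0): missed growth 5 × 12/52.18 = 1.15 cm; (141.15/140)^2.0 − 1 = 1.65%; × 90 = 1.5 points.
- High end (g = 7, h = 125, k = 2.4): missed growth 7 × 12/52.18 = 1.61 cm; (126.61/125)^2.4 − 1 = 3.12%; × 90 = 2.8 points.

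**Other gaps, same formula and inputs**

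| Gap | Overstatement at ppFEV₁ 90, affected visit |
|---|---|
| 4 weeks | 0.5–0.9 points |
| 8 weeks | 1.0–1.9 points |
| 12 weeks | 1.5–2.8 points |
| 24 weeks (two heights missed in a row) | 3.0–5.7 points |

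**Wider assumptions.** Let growth be 4–8 cm a year, current height H 115–150 cm, k 2.0–3.0 and true ppFEV₁ 70–100, and compute ppFEV₁ × [(H / (H − g × w/52))^k − 1]. A 12-week gap then gives 0.9–5.0 points. The central case (6 cm a year, 130 cm, k = 2.5, ppFEV₁ 90) has 1.38 cm of missed growth and gives 2.4 points. The sign is positive in every combination with growth above zero.

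**Effect on a visit mean.** This is the error per affected visit times the share of subjects affected. With the central 12-week value of 2.44 points:
- 1% of heights missing: 0.01 × 2.44 = 0.02 points
- 5%: 0.05 × 2.44 = 0.12 points
- 10%: 0.10 × 2.44 = 0.24 points

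These rates are illustrative. Using the narrower 1.5–2.8 points instead, 5% missing gives 0.07–0.14.

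**The case against.** The strongest objection is that the rule will seldom operate. Height ("Measured with shoes off (Section 11.4.4") and spirometry ("Performed pre-bronchodilator, before the AM dose, and at approximately the same time at each visit (Section 11.2.3") are scheduled together, and the main analysis is clinic-only, so bias needs a clinic visit with usable spirometry but no height. That stands, and it is why the expected effect on a mean is small.

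A reader might infer that home visits will usually lack a height. The documents do not support that. Protocol 9.1.6 allows in-home assessments other than MBW; Addendum 1.0 lists height among in-home measurements; Addendum 2.0 lets subjects or caregivers measure it. Addendum 3.0 applies both to this study as applicable. Home height is permitted rather than required, however, so a home FEV₁ could still arrive without a same-day height.

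A reader might also infer that a carried height is at least 12 weeks old after Week 24. Twelve weeks is the typical gap, not a minimum: visit windows, the ETT Visit and unscheduled visits can shorten it, and a Week 96 height carried to Safety Follow-up would be about 4 weeks old.

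Nor does the error always favour the drug. A stale parent-study baseline height inflates baseline ppFEV₁ and understates the change. With no growth the error is zero, and over short gaps measurement error can outweigh growth. If height measurement error has an SD of 0.3–0.5 cm (assumed) and growth is 6 cm a year, a height carried 4 weeks would equal or exceed the one that would have been measured in about 14–26% of cases, falling to 0.1–2.5% at 12 weeks.

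Finally, it is tempting to say that stale heights will distort the comparison of home with clinic spirometry. SAP 8.3.3.2 does not name the metric. If the comparison uses FEV₁ in litres, height plays no part.

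None of this makes the carried height correct where the rule does apply.

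**Conclusion.** The point holds as a minor one. For a growing child with a missing post-baseline height, the stated rule on average overstates ppFEV₁ and its change from baseline, by about 1.5–2.8 points for a 12-week gap at ppFEV₁ 90. That range rests on the assumed growth, height and exponent; the direction needs only that the child has grown and that predicted FEV₁ rises with height.

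The likely effect on a visit mean is of the order of 0.1 points, conditional on an assumed 5% of missing heights. ppFEV₁ is listed among the other endpoints of an open-label safety extension. The documents do not support a claim that the main ppFEV₁ results would be materially biased. The optional analysis with home spirometry may be more exposed, to the extent that home values come without a height.

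**What to change.** Replace the height rule in Appendix C as follows:

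1. If height is missing at a spirometry visit, interpolate linearly by date between the nearest measured heights before and after, including parent-study heights.
2. If there is no later height, carry forward the height-for-age z-score from the last measured height and convert it to a height at the visit age. The SAP already derives height z-scores (8.2.2 and Appendix A).
3. Report, by visit and by clinic or home source, how many ppFEV₁ values rest on an imputed height.

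This needs a few lines of SAP text and minor programming, and the SAP can be amended before database lock. There are two small drawbacks. An interpolated value can change between data cuts when a later height arrives, which matters if the sponsor uses the interim analyses that protocol 12.4 allows. The rule may also differ from the parent study's, whose SAP is not among these documents. Apply the same rule to any parent-study ppFEV₁ results shown alongside, or footnote the difference.

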Appendix D: Imputation Rules for Missing AE dates

Imputation rules for missing or partial AE start date are defined below. If the imputed AE start date is before the study informed consent/assent date, the AE start date will be imputed using the study informed consent/assent date.

- **If only Day of AE start date is missing:**

- If the full (or partial) AE end date is NOT before the first dose date of the Treatment Period or AE end date is missing, then
 - if AE start year and month are equal to the month and year of first dose date of the Treatment Period, then impute the AE start day as the day of first dose date of the Treatment Period;
 - else impute the AE start day as 1.
- else impute the AE start day as 1.

Compare the imputed AE start date with TE period to determine whether the AE is pretreatment AE, TEAE or post-treatment AE.

- **If Day and Month of AE start date are missing:**

- If the full (or partial) AE end date is NOT before the first dose date of the Treatment Period or AE end date is missing, then
 - if AE start year is equal to the year of first dose date of the Treatment Period, then impute the AE start month and day as the month and day of first dose date of the Treatment Period;
 - else impute the AE start month as January and day as 1.
- else impute the AE start month as January and day as 1.

Compare the imputed AE start date with TE period to determine whether the AE is pretreatment AE, TEAE or post-treatment AE.

- **If Year of AE start date is missing:**

If the year of AE start is missing or AE start date is completely missing then query site and

- If the full (or partial) AE end date is NOT before the first dose date of the Treatment Period or AE end date is missing, then impute the AE start date as the first dose date of the Treatment Period;
- else impute the AE start date as the informed consent/assent date.

Imputation rules for partial AE end date are defined below:

- Impute the AE end date as min (the last day of the month, end of study participation) if day is missing, or min (Dec, end of study participation) if month is missing.

